9.6.2 Laboratory Test Results

The analyses of safety laboratory endpoints will include summary statistics (actual value and change or percent change from baseline for each laboratory parameter) over time by visit for the 6-month treatment period. Shifts in grades based on Common Terminology Criteria for Adverse Events (CTCAE) v3.0 of safety laboratory values between the baseline and the worst on-study value through Month 6 will be tabulated. Subject incidence of worst postbaseline calcium corrected by albumin CTCAE grades decreases will also be summarized. The percentages of subjects with laboratory toxicities \geq grade 3 CTCAE will be summarized.

Graphs showing central tendency and dispersion of the absolute values and percent changes from baseline by visit will also be provided for the following laboratory parameters: calcium corrected by albumin, phosphorus and alkaline phosphatase.

Drug-induced liver injury will be assessed by evaluating subjects for Hy's Law. Hy's law laboratory criteria are defined as aspartate transaminase or alanine transaminase > 3 times upper limit of normal (ULN), total bilirubin > 2 times ULN, and alkaline phosphatase < 2 times ULN assessed within 7 days. Subjects who meet these Hy's law laboratory criteria on study will be further evaluated to assess whether there exist underlying conditions or concomitant medications which may explain the elevation in laboratory analytes in order to assess whether these cases are true Hy's law cases.

9.6.3 Vital Signs

The analyses of vital signs will include summary statistics over time by actual treatment received.

9.6.4 Physical Measurements

The analyses of physical measurements will include summary statistics over time by actual treatment received.

9.6.5 Antibody Formation

The incidence and percentage of subjects who develop anti-romosozumab antibodies (binding and, if positive, neutralizing) at any time through Month 6 will be tabulated by treatment group for primary analysis. This analysis will be repeated to further include all

testing results from samples collected during the 3-month follow-up period at the time of the final analysis.

The subject incidence of injection site reaction, adverse events potentially associated with hypersensitivity, and adverse events corresponding to the MedDRA high level group term of autoimmune disorders will be provided by binding and neutralizing anti-romosozumab antibody status.

9.6.6 Exposure to Investigational Product

Descriptive statistics will be produced to describe the exposure to IP by treatment group. A partial dose will be counted as one dose in the summary of exposure to investigational product.

9.7 Other Analyses

9.7.1 Analyses of Pharmacokinetic or Pharmacokinetic/Pharmacodynamic Endpoints

Individual and mean serum romosozumab concentration-time data will be tabulated and presented graphically using nominal times. Descriptive statistics will be provided for romosozumab serum concentrations at each time point. The data set will be analyzed using the current version of Phoenix WinNonlin within the Pharsight Knowledgebase System data repository. Romosozumab serum concentrations with values below the lower limit of quantification will be set to zero for analysis. Reasons for excluding any data from the pharmacokinetic analyses will be provided. These analyses will be performed by the Clinical Pharmacology Modeling and Simulation group.

10. Changes From Protocol-specified Analyses

Table 10-1 of protocol version 1.0 dated 10 August 2017 states that the non-inferiority margin is based on the treatment difference:

$$(\mu_{\text{romosozumab HCP PFS}} - \mu_{\text{romosozumab self-administration AI/Pen}}).$$

However, the noninferiority margin will be based on:

$$(\mu_{\text{romosozumab self-administration AI/Pen}} - \mu_{\text{romosozumab HCP PFS}})$$

This is reflected in Table 3-1 of this statistical analysis plan and in [Section 7.2](#).

According to the Schedule of Activities in Protocol version 1.0 (Table 2-1) physical measurements (height and weight) will be assessed at baseline, month 3, and month 6. However, physical measurements at month 3 were not collected. Therefore, summaries of physical measurements will not include month 3.

11. Literature Citations / References

Van Elteren P.H. (1960) On the combination of independent two-sample test of Wilcoxon, Bulletin of the International Statistical Institute, 37, 351-361.

12. Appendices

Appendix A. Technical Detail and Supplemental Information Regarding Statistical Procedures and Programs

For the baseline assessment (excluding DXA), regardless of the width of the visit window, if there are multiple records within a Baseline window, the record that is the closest to and on or prior to Study Day 1 will be considered as the baseline value.

For the post-baseline assessment, if more than 1 visit falls within the defined window, the result from the visit closest to the target day will be used. If 2 evaluations are of the same distance from the target day, the result from the later visit will be used. If more than one evaluation on the same date, the average of the results will be used. Only laboratory results collected from the central laboratory will be averaged in the case of duplicate results.

To allow for variations in scheduling, the following visit windows will be used to assign evaluations to a most appropriate nominal visit for analysis and summarization.

Furthermore, there will be no gaps between visit windows in order to include as many data points as possible for summarization.

Spine and Hip DXA Scans, Physical Measurements^b

Nominal Visit	Target Day	Window Definition (Study Day)
Baseline ^a	1	Last evaluation prior to or on Study Day 1
Month 6	183	≥ Study Day 2

^a If results from baseline DXA are not available, the results from scans taken on or before Study Day 14 will be considered baseline values and not the Month 6 values.

^b Protocol indicates physical measurements will be assessed at month 3, however the data is not collected at month 3.

Serum Romosozumab Levels and Laboratory Assessments (Chemistry)

Nominal Visit	Target Day	Window Definition (Study Day)
Baseline	1	Last evaluation prior to or on Study Day 1
Month 1 ^a	31	Study Day 2 to 61
Month 3	92	Study Day 62 to 137
Month 6	183	≥ Study Day 138

^a Any assessment done on Study Day 1 but after the administration of the investigational product will be classified into Month 1.

Vital Signs, and Laboratory Assessments (Hematology)

Nominal Visit	Target Day	Window Definition (Study Day)
Baseline	1	Last evaluation prior to or on Study Day 1
Month 3	92	Study Day 2 to 137
Month 6	183	≥ Study Day 138

BTMs (sCTX and P1NP)

Nominal Visit	Target Day	Window Definition (Study Day)
Baseline	1	Last evaluation prior to or on Study Day 1
Month 1	31	Study Day 2 to 61
Month 6	183	≥ Study Day 62

Antibody Assessments

Nominal Visit	Target Day	Window Definition (Study Day)
Baseline	1	Last evaluation prior to or on Study Day 1
Month 1 ^a	31	Study Day 2 to 61
Month 3	92	Study Day 62 to 137
Month 6	183	Study Day 138 to 229
Month 9	275	≥ Study Day 230

^a Any antibody assessment done on Study Day 1 but after the administration of the investigational product will be classified into Month 1.

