7.1 Treatment Procedures

7.1.1 Investigational Products

Table 7-1. Study Treatments

Study Treatment Name	Amgen Investigational Product:	
	Romosozumab ^a in PFS	Romosozumab ^a in AI/Pen
Dosage Formulation	Romosozumab will be presented in a box containing 2 PFS. Each PFS will contain 1.17 mL of 90 mg/mL romosozumab.	Romosozumab will be presented in a box containing 2 AI/Pens. Each AI/Pen will contain 1.17 mL of 90 mg/mL romosozumab.
Unit Dose Strength(s)/ Dosage Level(s) and Dosage Frequency	210 mg QM (2 PFS)	210 mg QM (2 AI/Pens)
Route of Administration	SC injection	SC injection
Accountability	The amount administered, date and time of administration, and box number of romosozumab are to be recorded on each subject's CRF.	The amount dispensed, amount returned, amount self-administered (ie, full, partial, none, unknown), date dispensed, date returned, the date of self-administration, and box number of romosozumab are to be recorded on each subject's CRF.

Study Treatment Name	Amgen Investigational Product:	
	Romosozumab ^a in PFS	Amgen Investigational Product: Romosozumab ^a in AI/Pen

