5.2 Study Points of Reference

Baseline

The baseline measurement is defined as the last measurement prior to the first dose of IP. If the measurement is taken on the same day as the first dose and the exact measurement time relative to the first dose is unknown, it will be assumed to have been taken prior to the first dose of IP. If a subject does not receive IP, baseline is the closest recorded measurement on or prior to the randomization date. For baseline duplicate BMD taken on the same day, the baseline is obtained as the average of the measurements.

Note: If baseline result from DXA assessment is not available, the result assessed on or before Study Day 14 will be considered baseline.

Study Day 1

The first day of IP administration or the day of randomization for subjects who do not receive any dose of IP.

Study Day

The number of days from Study Day 1, inclusive:

Study Day = (Date of Interest – Date of Study Day 1) + 1

For days prior to Study Day 1:

Study Day = (Date of Interest – Date of Study Day 1)

Analysis Visit

To allow for variations in scheduling study visits, the analysis visit windows defined in [Appendix A](#) will be used to assign evaluations to the most appropriate nominal visit for analysis and summarization.

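### SAP Appendix A files a Day 1 sample drawn after the first dose as Month 1, which removes the antibody baseline and, on the listed dosing fields, could be applied unequally by arm

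*SAP*

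**What the plan says.** **Windows.** In each Appendix A window table the baseline row reads "Last evaluation prior to or on Study Day 1". The antibody Month 1 row covers Study Days 2 to 61 with target Day 31. Its footnote adds: "Any antibody assessment done on Study Day 1 but after the administration of the investigational product will be classified into Month 1". The table for romosozumab levels and chemistry has the matching footnote: "Any assessment done on Study Day 1 but after the administration of the investigational product will be classified into Month 1". The tables for hematology and bone turnover markers, also sampled on Day 1, have no such footnote. The SAP amendment log shows that both footnotes were added in version 2.0.

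**Same-day order.** SAP 5.2 defines baseline as the last value before the first dose. For a same-day sample, if "the exact measurement time relative to the first dose is unknown, it will be assumed to have been taken prior to the first dose".

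**Dosing records.** Protocol Table 7-1 states for PFS: "The amount administered, date and time of administration, and box number of romosozumab are to be recorded". For AI/Pen the list ends: "date dispensed, date returned, the date of self-administration, and box number of romosozumab are to be recorded". Protocol 7.6 repeats the AI/Pen list, again without a time.

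**Sampling.** Protocol Table 2-1 schedules the first antibody sample and the first drug-level sample on Day 1. Chemistry is also drawn at screening. Antibody samples are to be taken before dosing.

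**Endpoint.** SAP 9.6.5 tabulates "The incidence and percentage of subjects who develop anti-romosozumab antibodies (binding and, if positive, neutralizing) at any time through Month 6", and also breaks down injection site reactions, hypersensitivity and autoimmune events by antibody status. Neither document defines *develop*.

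**The concern.** An antibody detected on the day of a first injection was almost certainly present beforehand. Exclusion criterion 223 bars prior sclerostin antibody use only within the previous 12 months, so earlier exposure, and possibly a pre-existing antibody, can be present at entry. The footnote nevertheless turns such a result into an on-study finding and deletes the only scheduled baseline against which it could be judged.

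The footnote also works only if the order of draw and dose is known. On the fields the protocol lists, that order can be established from clock times for PFS but not for AI/Pen, where the SAP 5.2 default would return the sample to baseline. Antibody incidence is a named secondary safety endpoint in a comparison of two devices. It has no formal test, so readers will compare the raw percentages. A classification convention should not depend on the arm.

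**Working it through.** **1. The plan's own windows.** The cut-offs are midpoints between target days:
- (31 + 92)/2 = 61.5, stated cut-off 61
- (92 + 183)/2 = 137.5, stated cut-off 137
- (183 + 275)/2 = 229, stated cut-off 229

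The antibody windows reproduce. Day 1 lies outside the Month 1 window and enters it only through the footnote.

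**2. Tracing one Day 1 antibody sample through the rules**

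| Case | PFS | AI/Pen |
|---|---|---|
| Drawn before the dose (as planned) | Baseline | Baseline |
| Drawn after the dose; sample time in the data; dose time only as listed | Month 1, no baseline left | Baseline, by the SAP 5.2 default |
| Drawn after the dose; sample time not in the data | Baseline, by the default | Baseline, by the default |
| Drawn after the dose; order known in both arms | Month 1, no baseline left | Month 1, no baseline left |

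The arms diverge only in the second row. The lost baseline and the implausible post-baseline positive also occur in the fourth row, in both arms.

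**3. When a Day 1 value represents Month 1.** Appendix A takes the result nearest the target day, and the later one in a tie. The distance from Day 1 to Day 31 is 30 days. A Month 1 visit within its window is at most about 7 days from target, or 14 at the outer dosing limit. A sample on Day 61 is also 30 days away and wins the tie. So the Day 1 value is used only when nothing else falls in Days 2 to 61. For antibody incidence at any time, the Month 1 label is irrelevant; what matters is baseline versus post-baseline.

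**4. Size.** The documents give no antibody rate and no count of late Day 1 draws, so both are assumed. Let d be the share of Day 1 samples drawn after the dose and q the share of those that are positive. With about 130 subjects per arm (Protocol 5.2):
- one subject = 1/130 = 0.77 percentage points
- expected PFS subjects reclassified = 130 × d × q
- chance of at least one = 1 − (1 − d × q)^130

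| d | q | Expected subjects | Percentage points | Chance of at least one |
|---|---|---|---|---|
| 0% | any | 0 | 0 | 0 |
| 2% | 5% | 0.13 | 0.10 | 0.12 |
| 5% | 5% | 0.33 | 0.25 | 0.28 |
| 10% | 10% | 1.30 | 1.00 | 0.73 |

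**5. Direction.** This depends on the missing definition.
- If any post-baseline positive counts, a late positive PFS sample adds a case. Its AI/Pen counterpart adds one only if a later sample is also positive.
- If a negative baseline is required, a PFS woman without a baseline may never be counted, even if she converts later. That lowers PFS incidence. The formula in step 4 then applies with q read as the share of late-drawn women who convert later, which is equally unknown.

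**The case against.** The strongest reply is that the situation should hardly arise. Protocol Table 2-1 and Appendix 2 place blood draws before dosing, and the injection is the last procedure of the Day 1 visit in both arms. Staff supervise the first AI/Pen dose. No passage reports a late sample. Safety results are descriptive, and the comparison of BMD is untouched. All of this stands and limits the point to a small one.

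Several stronger readings are tempting but not supported:
- *Antibody incidence is classified differently by arm.* This needs a draw out of order, an affected result, the sample time in the analysis data, and no usable dose order for AI/Pen. The documents establish none of these as having happened.
- *The footnote can be applied only to PFS.* This is an inference from field lists. The CRF is not among the documents, and SAP 5.2 turns on relative order. Since collection time goes into the medical record and staff watch the first self-injection, order may be recoverable from source.
- *Any error favors AI/Pen.* Step 5 shows that the direction can reverse.
- *The antibody table contradicts itself.* The footnote is an explicit exception to the Month 1 row, and it agrees with the pre-dose baseline definition in SAP 5.2.
- *Month 1 drug levels and chemistry are generally contaminated.* The nearest-day rule prevents this unless Days 2 to 61 are empty. Chemistry also keeps its screening value as a baseline.

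What remains is that the rule, followed as written, gives an implausible antibody classification and can do so unequally.

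**Conclusion.** The point holds as a limited flaw in a stated rule. For a Day 1 sample drawn after dosing, Appendix A removes the only scheduled antibody baseline and treats a same-day positive as post-baseline. For drug level or chemistry it lets a Day 1 value represent Month 1 when no other sample exists in the window. On the listed dosing fields, the filing could differ between arms.

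The expected size is about 0 to 1 subject, at 0.77 percentage points each. This rests on assumed late-draw rates of 0 to 10% and positivity of up to 10%; the documents give neither figure. It also assumes that sample times reach the analysis data and that no AI/Pen dose time is held outside the listed fields. The direction is open until *develop* is defined. The noninferiority conclusion on lumbar spine BMD does not depend on any of this.

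**What to change.** Change SAP wording only:
1. **Antibodies.** Use the Day 1 sample as baseline in both arms, whether drawn before or after the dose. State this as an exception to the pre-dose definition in SAP 5.2 and 9.1, and list it in SAP Section 10, because Protocol 10.3.2.1 uses the same definition. No dose time is needed, so the arm difference in antibody classification becomes zero.
2. **Drug levels and chemistry.** Do not use a Day 1 value known to be post-dose as Month 1. List it and leave it out of the baseline and Month 1 summaries; baseline chemistry falls back to screening.
3. **Definition.** State in SAP 9.6.5 that *develop* means a post-baseline positive in a subject who was negative at baseline.

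The cost is small. A few antibody baselines may have been drawn shortly after dosing and should be flagged in a listing. Item 2 still relies on SAP 5.2 where the order is unknown, so it does not fully equalize the arms for drug levels and chemistry. Adding a CRF time field for the first self-injection is not proposed: the amendment is dated 08 May 2019 and the primary-analysis snapshot was planned for 20 June 2019, after all subjects could reach Month 6, so Day 1 dosing was essentially over.

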Appendix B. Reference Values/Toxicity Grades

The Common Terminology Criteria for Adverse Events (CTCAE) are available at the following link:

http://ctep.cancer.gov/protocolDevelopment/electronic_applications/docs/ctcae3.pdf.

Appendix C. Cardiovascular Medical History Risk Group Identification Strategy

Cardiovascular Medical History Risk Group	Search Strategy
Hypercholesterolemia	Dyslipidemia SMQ (narrow)
Hypertension	Hypertension SMQ (narrow)
Diabetes	Hyperglycaemia SMQ (narrow)
Cardiovascular Disease	Cardiac Disorders SOC and Vascular Disorders SOC
Central Nervous System Vascular Disorder	Central Nervous System Vascular Disorders HLGT
Ischemic heart disease	Ischemic heart disease SMQ (narrow)
Central nervous system haemorrhages and cerebrovascular conditions	Central nervous system haemorrhages and cerebrovascular conditions SMQ (narrow)
Atrial fibrillation or atrial flutter	Preferred terms
Stroke	Stroke AMQ (see Appendix D)
Myocardial infarction	Myocardial infarction SMQ (narrow)
Coronary artery disease	Coronary artery disorders HLGT
Revascularization	Coronary revascularization AMQ (see Appendix E ; narrow)
Cerebrovascular disease	Central nervous system vascular disorders SMQ (narrow)
Heart Failure	Cardiac failure SMQ (narrow)
Ischemic stroke or TIA	Ischaemic central nervous system vascular conditions SMQ (narrow)

Appendix D. Search Terms for History of Stroke

Basal ganglia haemorrhage
Basal ganglia infarction
Basal ganglia stroke
Basilar artery occlusion
Brain stem embolism
Brain stem haemorrhage
Brain stem infarction
Brain stem microhaemorrhage
Brain stem stroke
Brain stem thrombosis
Central nervous system haemorrhage
Cerebellar artery occlusion
Cerebellar artery thrombosis
Cerebellar embolism
Cerebellar haemorrhage
Cerebellar infarction
Cerebellar microhaemorrhage
Cerebellar stroke
Cerebral arteriovenous malformation haemorrhagic
Cerebral artery embolism
Cerebral artery occlusion
Cerebral artery thrombosis
Cerebral haemorrhage
Cerebral haemorrhage foetal
Cerebral haemorrhage neonatal
Cerebral infarction
Cerebral infarction foetal
Cerebral microembolism
Cerebral microhaemorrhage
Cerebral septic infarct
Cerebral thrombosis
Cerebral vascular occlusion
Cerebrovascular accident
Embolic cerebral infarction
Embolic stroke
Haemorrhage intracranial
Haemorrhagic cerebral infarction
Haemorrhagic stroke
Haemorrhagic transformation stroke
Intracranial tumour haemorrhage
Intraventricular haemorrhage
Intraventricular haemorrhage neonatal
Ischaemic cerebral infarction
Ischaemic stroke
Lacunar infarction
Lacunar stroke
Migrainous infarction
Perinatal stroke
Periventricular haemorrhage neonatal
Pituitary haemorrhage
Post procedural stroke

Post stroke depression
Putamen haemorrhage
Stroke in evolution
Subarachnoid haemorrhage
Subarachnoid haemorrhage neonatal
Subdural haemorrhage
Subdural haemorrhage neonatal
Thalamic infarction
Thalamus haemorrhage
Thrombotic cerebral infarction
Thrombotic stroke
Transverse sinus thrombosis
Vertebral artery occlusion
Vertebral artery thrombosis

Appendix E. Search Terms for History of Revascularization

Preferred Term	Scope
Aortic aneurysm repair	Narrow
Aortic bypass	Narrow
Aortic stent insertion	Narrow
Endarterectomy of aorta	Narrow
Intra-thoracic aortic aneurysm repair	Narrow
Arterectomy	Narrow
Arterectomy with graft replacement	Narrow
Arterial aneurysm repair	Narrow
Arterial bypass operation	Narrow
Arterial graft	Narrow
Arterial stent insertion	Narrow
Carotid angioplasty	Narrow
Carotid artery bypass	Narrow
Carotid artery stent insertion	Narrow
Carotid endarterectomy	Narrow
Carotid revascularisation	Narrow
Cerebral endovascular aneurysm repair	Narrow
Cerebral revascularisation	Narrow
Coronary angioplasty	Narrow
Coronary arterial stent insertion	Narrow
Coronary artery bypass	Narrow
Coronary endarterectomy	Narrow
Coronary revascularisation	Narrow
Endarterectomy	Narrow
Intra-cerebral aneurysm operation	Narrow
Mesenteric artery stent insertion	Narrow
Percutaneous coronary intervention	Narrow
Peripheral artery angioplasty	Narrow
Peripheral artery bypass	Narrow
Peripheral artery stent insertion	Narrow
Peripheral endarterectomy	Narrow
Pulmonary endarterectomy	Narrow
Renal artery angioplasty	Narrow
Renal artery stent placement	Narrow
Aneurysm repair	Narrow
Aneurysmectomy	Narrow
Angioplasty	Narrow
Arteriovenous graft	Narrow
Peripheral revascularisation	Narrow
Thrombectomy	Narrow
Thromboembolectomy	Narrow
Vascular graft	Narrow
Vascular stent insertion	Narrow

SAP Amendment 1

Protocol Title: A Randomized, Multicenter, Open-label, Parallel Group Study in Postmenopausal Women With Osteoporosis to Evaluate the Noninferiority of Subject-administered Romosozumab via Autoinjector/Pen vs Healthcare Provider-administered Romosozumab via Prefilled Syringe

AMG 785/Romosozumab Amgen Protocol Number 20150120

Protocol Date: 10 August 2017

SAP Version Number 2.0

SAP Amendment Date 08 May 2019

The statistical analysis plan for this study was amended to clarify analyses to be performed during the upcoming primary analysis for this study (snapshot planned for 20 June 2019).

Editorial changes were also implemented throughout the document.

Description of Changes:

[Global](#)

Minor corrections throughout the document (eg, correcting typographical and formatting errors).

Header date was replaced with 08 May 2019.

Document version was replaced with v2.0.

[5.1 Basic Definitions](#)

Add:

Treatment-emergent Adverse Events

Adverse Events (AEs) starting on or after first dose of investigational product as determined by the flag indicating if the adverse event started prior to the first dose on the Adverse Events Summary CRF and up to the end of study date.

Serious adverse events (SAEs) starting on or after first dose of investigational product as determined by the flag indicating if the adverse event started prior to the first dose on the Adverse Events Summary CRF and up to the end of study date.

[5.2 Study Points Reference](#)

Replace:

Baseline

The baseline measurement is defined as the last measurement prior to the first dose of investigational product. If the measurement is taken on the same day as the first dose and the exact measurement time relative to the first dose is unknown, it will be assumed to have been taken prior to the first dose of investigational product. If a subject does not receive investigational product, baseline is the closest recorded measurement on or prior to the randomization date. For baseline duplicate BMD, the baseline is obtained as the average of the measurements taken prior to the first dose of investigational product.

Note: If baseline result from lateral spine x-ray, DXA, or QCT assessment is not available, the result assessed on or before Study Day 14 will be considered baseline.

With:

The baseline measurement is defined as the last measurement prior to the first dose of IP. If the measurement is taken on the same day as the first dose and the exact measurement time relative to the first dose is unknown, it will be assumed to have been taken prior to the

first dose of IP. If a subject does not receive IP, baseline is the closest recorded measurement on or prior to the randomization date. For baseline duplicate BMD taken on the same day, the baseline is obtained as the average of the measurements.

Note: If baseline result from DXA assessment is not available, the result assessed on or before Study Day 14 will be considered baseline.

